A plethora of indices and tools have been studied and marketed to assess intravascular volume status with only a few proven reliable with reproducible results. Based on pre-fluid challenge values, several of these tools have been used to predict who may benefit from additional fluid (fluid responders). Alternatively, some of these tools have been used to distinguish fluid responders from non-responders based on changes in pre- and post-fluid challenge values. Among these tools, the pulmonary artery catheter provides measurements of both left and right heart pressures which can be applied to calculate the cardiac output (CO) and stroke volume (SV). Changes in these values (e.g. an increase in the stroke volume by 10%) between pre- and post-fluid challenge have been used to define fluid responders. This devise, however, is invasive with several significant risks, and therefore is rarely used in children. Echocardiography, on the other hand, is a non-invasive bedside study also used to assess CO and SV but is expensive and requires trained echosonographers for application. Further, because a transthoracic probe is required to obtain the images, application in the operating room is difficult as the chest is often in the operating field limiting access to the echosonographer. Lastly, the esophageal aortic blood flow device (CardioQ-EDM, Deltex Medical, Chichester, UK) has been found in multiple adult and pediatric studies to reliably distinguish fluid responders from non-responders intensive care unit (ICU) and operating room [2-6]. Much like an orogastric tube, this device is simply placed by a provider in the patient's esophagus and uses Doppler waveforms to measure aortic blood flow velocities (**Figure 1**). Variations in the amplitude of peak velocities has been shown to corelate with intravascular volume status[2-6]. Specifically, a change in the peak velocity by greater than 10% between pre- and post-fluid challenge values has

Protocol #: 18-2513

[figure not shown]
PI: [name]

Version date: 07/01/2019

[figure not shown]
been shown to accurately distinguish those who are fluid responsive from those who are not with similar accuracy to echocardiography and pulmonary artery catheter readings[7].

Figure 1

A

B

Legend: A) Illustration of CardioQ-EDM position. In children age 15 years and younger, the device is introduced through the oral cavity. B) Correct placement confirmed by descending aortic waveform.

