Objective measures to guide resuscitation became mainstream with the introduction of the pulmonary artery catheter in 1970 [11]. Over the ensuing decades, several randomized control trials demonstrated that the use of pulmonary artery catheters did not incur a survival advantage. In fact, the complexity inherent in placing, operating, and interpreting data from this tool is not without risk. Thus, in large part, these invasive devices have fallen out of favor [12-14]. There has since been a focus on developing minimally invasive and non-invasive tools to gauge intravascular volume status in order to accurately direct resuscitation.

Several of these techniques rely on cardiopulmonary interactions with the cyclic variations of intra-thoracic pressure produced by ventilation. In a mechanically ventilated patient, changes in intra-thoracic pressures are transmitted to the right ventricle with increased pressure during inspiration and decreased pressure during exhalation. In patients who are intravascularly deplete, these pressure shifts lead to larger variations in measured parameters such as pulse pressure, IVC collapsibility, and plethysmography throughout the respiratory cycle. **Figure 2** describes the variation in pulse pressure which is represented by ΔPs . Plethysmography variation and CI are derived in a similar fashion using corresponding waveforms with the notion that more variation correlates with less intravascular volume.

Figure 2

Pp_{min} , minimal arterial pulse pressure; Pp_{max} , maximal arterial pulse pressure; Ps_{min} , minimal arterial systolic pressure; Ps_{max} , maximal arterial systolic pressure; ΔPs , pulse pressure variability. From Vasodilation increases pulse pressure variation, mimicking hypovolemic status in rabbits. Westphal GA, Goncalves AR, Bedin A et al., 2018, *Clinics*[15].

Tools and indices available to measure intravascular volume status are numerous with the most frequent utilized ones described in **Table 2**. These indices range from simply measuring the systolic blood pressure to using computer generated algorithms in order to calculate a CRI. This armamentarium has vast applicability, but the predictive utility is variable, influenced by several confounders, and must be applied in the appropriate clinical setting.

Table 2: Intravascular Volume Status Measurements

INVASIVE DEVICES	
SWAN-GANZ CATHETER	CO, SVR, SV, LVEDAI, GEDVI, CVP, PCWP
CENTRAL VENOUS CATHETERS	CVP, SvO_2 , ΔpCO_2

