non-responders for Δ VPeak was 0.94 [18]. While the optimal Δ VPeak varied from 7-20% among studies, one of the larger series using a Δ VPeak of 10% as a threshold found the sensitivity and specificity to be 100% in distinguishing fluid responders based on aortic velocity-time integrals identified by transthoracic echocardiogram [7]. Based on these results, we plan to define fluid responders as those who have $>10\%$ Δ VPeak between pre- and post-fluid challenge.

Bedside evaluation of the IVC to calculate the CI is a commonly used tool in adults [19, 20]. It serves as a surrogate to measure preload variation induced by mechanical ventilation. The technique requires limited ultrasonographic experience often at the critical care or anesthesia fellow level. In pediatrics, the predictive utility of IVC CI has only been evaluated in small series with conflicting results [21].

The CRI is another non-invasive devise using a photoplethysmographic probe (CipherOx-CRI) placed on the index finger. Based on data gathered from the probe, a computer-generated algorithm is then used to calculate a number between zero and one, referred to the CRI (Figure 3) [22]. The CRI correlates to one's intravascular volume status and proximity to hemodynamic collapse [23].

Figure 3

Legend: CRI, compensatory reserve index. CRI=1 is normovolemia and CRI=0 is the point at which the patient is at highest risk for hemodynamic decompensation.

Confounding factors that can influence dynamic measurements must also be considered. For instance, cardiac arrhythmias, small tidal volumes, spontaneous respiration, and high positive end-expiratory pressure have been found to decrease the predictive utility of pulse pressure variability and IVC CI [24-26]. Thus, it is paramount to use and apply these measurements in the appropriate clinical setting. Presumably, the influence confounding variables have on the predictive utility of these indices in children is similar to that of adults, however, comparative analyses have not been performed. Thus, when interpreted in the appropriate clinical context, these minimally and non-invasive devices are tools available to guide a balanced fluid resuscitation; however, while small series exist in various pediatric populations, validation is necessary in order to apply these tools in hypovolemic children with significant blood loss.

Protocol #: 18-2513

PI: [name]

Version date: 07/01/2019

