Hypothesis II: CRI and collapsibility index will reliably predict fluid responsive patients with an approximate area under the receiver operating characteristic curve (AUROC) of 0.9 while other indices will have a lower predictive accuracy.

Aim III: Evaluate confounding variables that may influence predictive measures outlined in Aim II.

Hypothesis III: Confounding variables that may decrease the predictive accuracy of indices described in Aim II include spontaneous breathing over the ventilator, minimal blood loss, and hypothermia

4. Materials and Methods:

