4.3 Patient recruitment

Patients will be identified by the PI based on communication with the craniosynostosis clinic team. Parents/guardians of eligible candidates will be approached by a study team member at their pre-operative appointment or on the day of surgery for voluntary participation. If recruitment is insufficient (<70%), a \$20 gift card will be used as incentive for study participation. Funding will be provided by the division of pediatric surgery if this is necessary.

4.3.1 Population: Children older than 3 months and younger than 2 years of age who undergo cranial vault reconstruction in the supine position will be included. Children with associated syndromes will be included as long as they do not have known underlying cardiac abnormalities. Consent will be translated into Spanish as well for those in whom it is indicated.

4.3.2 Exclusion Criteria: Children with known underlying cardiac anomalies or cardiac arrhythmias, infants younger 3 months of age or greater than 2 years of age. In addition, children weighing less than 3 kg will be excluded at the recommendation of the manufacturer. While vasopressor (epinephrine, norepinephrine, and/or vasopressin) support is not a contraindication, fluid boluses administered during dosage adjustments will be excluded from analysis. Patients who are placed in the prone position for surgery will also be excluded given the difficulty with obtaining a window to measure the IVC CI and possible effect on reported measurements. Additionally, if abnormal anatomy is discovered while assessing the IVC, these children will also be excluded from analysis.

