4.4 Definitions

- *Bolus* – 10 - 20 ml/kg fluid (isotonic crystalloid, colloid, or blood product) up to 1 L and given within a 10 minutes period
- *Fluid responders* – Children who have a pre- and post-fluid challenge $\Delta VPeak > 10\%$ calculated using the equation ($\Delta VPeak_{pre} = (VPeakmax_{pre} - VPeakmin_{pre}) /$

Protocol #: 18-2513

PI: [name]

Version date: 07/01/2019

$$[(V_{peakmean_{pre}})] - (\Delta V_{Peak_{post}} = (V_{Peakmax_{post}} - V_{Peakmin_{post}}) / [(V_{peakmean_{post}})] \times 100$$

- *Multiple fluid challenges* – If more than one fluid bolus is administered at least 30 minutes apart, they will be reported as individual events
- *Pre-bolus measurements* – Hemodynamic measurements will be calculated or recorded three times thirty seconds apart and averaged just before a bolus is administered. Cine loops from IVC measurements will be recorded three times, thirty seconds apart for post-hoc CI calculation. Peak aortic velocity and CRI will be recorded on the EDM monitor and averaged over 90 seconds.
- *Post-bolus measurements* - Hemodynamic measurements will be calculated or recorded three times and averaged five minutes after a bolus is completed. These measurements will be time and repeated in an identical fashion to pre-bolus measurements.

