2. After positioning the patient for surgery, the CardioQ-EDM device will be placed through the mouth into the esophagus by the PI or Co-investigators (Drs. [name] or [name]) and the aortic Doppler waveform will be confirmed. Additionally, the CipherOx-CRI finger probe will be placed, and a baseline IVC CI will be measured and recorded.
3. Baseline values and measurements (included in **Table 3**) will be recorded. Additionally, the baseline ΔV_{Peak} and CRI will be recorded.
4. A protocolized 10 mg/kg crystalloid fluid bolus will be administered
5. Two minutes after the bolus has completed, repeat EDM and CRI values will be recordings and a repeat abdominal ultrasound to measure the IVC CI will be obtained.
6. If an additional fluid bolus or blood transfusion is administered during the remainder of the procedure, steps 3 and 5 will be repeated.

4.6.1 Demographic Data: Age, weight, height, body mass index (BMI), gender, and ethnicity will be collected from medical records.

4.6.2 Ventilator Data: pressure or volume control, tidal volume (ml/kg) and peak end-expiratory pressure (PEEP), peak inspiratory pressure (PIP), and spontaneously breathing.

4.6.3 CardioQ-EDM Data: Based on a validated internal nomogram derived from the child's age, height, and weight[27], peak velocities will be obtained from the Cardio-EDM monitor.

4.6.4 Fluid Data/Vasopressor Administration: Number, time, type, and volume of fluid/blood administered will be recorded in real time. Vasopressor agent, dose, and time administered will also be reported.

4.6.5 Waveform/Vital Data: As it is currently not possible to extract waveform data from the operating room monitors, we will record data in real time. Values listed below will be reported on an excel spreadsheet.

Parameters to measure:

All parameters will be measured x 3 with 30 seconds between each measurement and averaged

- Systolic blood pressure (measured by arterial line)
- Mean arterial pressure (calculated from arterial line)
- Heart rate
- Pulse pressure variability (measured by arterial line) = acquired from arterial line
- Stroke volume variability – acquired from arterial line
- $\Delta V_{peak} = (V_{Peakmax} - V_{Peakmin}) / [(V_{peakmean}] \times 100$
- Compensatory reserve index – algorithmically generated
- Inferior vena cava collapsibility index = Maximum diameter (expiration) – minimum diameter (inspiration)/maximum diameter (expiration) in M mode

4.7 Data Blinding:

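### The responder label depends on ventilation at two time points, but the plan does not pair ventilator readings or handle boluses where ventilation changes between them, so the spontaneous-breathing part of Hypothesis III cannot separate index error from reference error

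*Combined protocol and SAP*

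**What the plan says.** Section 4.4 of the combined protocol and SAP defines fluid responders as "Children who have a pre- and post-fluid challenge $\Delta VPeak > 10\%$ calculated using the equation" that follows. The equation subtracts post-bolus from pre-bolus ΔVPeak, each being (maximum − minimum)/mean of peak velocity. The background says that several volume-status techniques rely on "cyclic variations of intra-thoracic pressure produced by ventilation".

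Ventilator information is collected. Section 4.6.2 lists "pressure or volume control, tidal volume (ml/kg) and peak end-expiratory pressure (PEEP), peak inspiratory pressure (PIP), and spontaneously breathing", and the Aim III table in section 5 carries ventilation variables as covariates. Neither place says whether they are read before the bolus, after it, or both. Step 5 of the day-of-surgery description says that "repeat EDM and CRI values will be recordings and a repeat abdominal ultrasound to measure the IVC CI will be obtained"; it does not mention the ventilator. Section 4.4 has post-bolus haemodynamic measurements repeated in the same way as the pre-bolus ones, also without naming ventilator fields.

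For one co-intervention the plan does protect the pre/post comparison. Section 4.3.2 states, for vasopressors, that "fluid boluses administered during dosage adjustments will be excluded from analysis".

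Hypothesis III in section 3 reads in part: "Confounding variables that may decrease the predictive accuracy of indices described in Aim II include spontaneous breathing over the ventilator". Minimal blood loss and hypothermia are its other two factors.

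**The concern.** A pre-to-post difference in respiratory variation isolates the effect of fluid only if the respiratory drive is the same at both readings. If settings change, or the child starts or stops breathing over the ventilator, ΔVPeak can move without any change in volume status, and the label can move with it.

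Two things are at stake. First, label error distorts the accuracy estimates of Aim II. Error unrelated to an index pulls its AUROC towards 0.5. Error shared with an index can raise it, and PPV, SVV and IVC CI respond to the same pressure swings. Second, Hypothesis III judges index accuracy under spontaneous breathing against a reference that spontaneous breathing can also disturb. A lower AUROC in those boluses could come from the index, the reference or both.

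**Working it through.** The plan gives no figure for this point, so there is nothing to reproduce. The inputs from the documents are the label and its 10% threshold (4.4), about half of children expected to respond (Hypothesis Ia), and a hypothesised AUROC of 0.9 for CRI and CI (Hypothesis II). The bolus lasts up to 10 minutes (4.4). The post-bolus reading comes 5 minutes later by section 4.4 but 2 minutes later by step 5, two statements that need reconciling. The window is therefore about 12 to 15 minutes. Rates of ventilator change and of label error are not in the documents; the values below are assumptions.

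**1. Can ventilation alone create the label?** Assume ΔVPeak is proportional to tidal volume and fluid has no effect. Section 4.4 subtracts, so the threshold reads as percentage points. From a pre-bolus value P, a fractional fall r in tidal volume gives a difference of P × r, which exceeds 10 when r > 10/P.

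| Pre-bolus ΔVPeak | Fall in tidal volume needed |
|---|---|
| 15 | over 67% |
| 20 | over 50% |
| 25 | over 40% |
| 30 | over 33% |

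If the threshold were a relative change, any fall above 10% would do.

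**2. Can it tip a borderline bolus?** Take P = 20. If fluid alone lowers ΔVPeak by 7 points (non-responder), the difference is 20 − 13(1 − r) = 7 + 13r, which exceeds 10 when r > 3/13 = 23%. If fluid alone lowers it by 13 points (responder), a rise r in tidal volume gives 20 − 7(1 + r) = 13 − 7r, which is 10 or less when r ≥ 3/7 = 43%. So smaller changes matter near the threshold.

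**3. What does label error do to the AUROC?** With 50% responders and symmetric label error f unrelated to the index, observed AUROC = 0.5 + (1 − 2f)(true AUROC − 0.5). From a true 0.90:

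| f | Observed AUROC |
|---|---|
| 5% | 0.86 |
| 10% | 0.82 |
| 15% | 0.78 |
| 20% | 0.74 |

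**4. Can the two explanations be told apart?** In a simulation of 400,000 draws, a true AUROC of 0.90 with 20% label error gave 0.741, and a true AUROC of 0.74 with a perfect label gave 0.740. The observed AUROC does not distinguish them.

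**5. Can the bias go upward?** Suppose fluid lowers ΔVPeak by 13 points in true responders and 7 in non-responders, with measurement noise of SD 1. A transient ventilation effect of SD s acts on the pre-bolus reading and on an index (noise SD 5) that carries no volume information. Label error is 1 − Φ(3/√(s² + 1)).

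| s (points) | Label error | AUROC, transient shared | AUROC, not shared |
|---|---|---|---|
| 2 | 9% | 0.56 | 0.50 |
| 3 | 17% | 0.64 | 0.50 |
| 5 | 28% | 0.77 | 0.50 |

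**6. Does planned adjustment help?** Section 4.8 screens confounders by their association with the label itself (p < 0.10), and no covariate is defined as a pre-to-post change. Adding covariates to a model of the label on the index does not correct a wrong label.

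**The case against.** Several stronger readings are tempting, and the documents do not support them.

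- A reader might infer that the protocol itself says ventilation degrades ΔVPeak. The background does say that "cardiac arrhythmias, small tidal volumes, spontaneous respiration, and high positive end-expiratory pressure have been found to decrease the predictive utility", but the sentence goes on to name only PPV and the collapsibility index. Extending this to ΔVPeak is an inference from the shared mechanism.
- A reader might infer that boluses with a ventilator change are kept by rule. The text is silent on them. Only spontaneous breathing is clearly meant to be in the data, since Hypothesis III and the Aim III table analyse it.
- A reader might infer that a change would go unnoticed because Aim III uses pre-bolus values. In that table the pre-bolus entry locates the outcome row; the ventilator covariates have no stated timing. An investigator is present throughout and completes a Data Collection Form for each bolus. That form and the Table 3 cited in step 3 were not in the text reviewed, so paired recording may exist there.
- A reader might infer that Hypothesis III fails as a whole. Minimal blood loss and hypothermia are not touched by this argument. The Aim III regression of index values does not use the label and can show whether ventilation shifts an index, although it does not test accuracy.

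There is partial mitigation. The post-induction bolus is analysed separately, ventilation may well be stable then, and paralysis is recorded. The background also describes a different quantity, saying that "a change in the peak velocity by greater than 10% between pre- and post-fluid challenge values has" been shown to identify responders. If that were the intended label, the mechanism would weaken, and the two definitions must be reconciled. Section 4.4 is the operative one.

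What remains after all this is that the text neither requires paired ventilator readings nor handles a change between them, and that adjustment cannot repair the reference.

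**Conclusion.** The concern holds in a limited form. The label is sensitive to ventilation at two time points, and the plan handles a change between them only for vasopressors. On the percentage-point reading, only large ventilator changes create a label unaided; smaller ones matter for borderline boluses. The overall effect on the AUROC cannot be sized, because the documents give no frequency of ventilator changes or spontaneous breaths. The figures above show what given error rates would do and do not predict them. They rest on proportionality to tidal volume, 50% responders and the assumed error structures.

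The firm consequence concerns the spontaneous-breathing part of Hypothesis III: lower accuracy there cannot be assigned to the index rather than the reference. This is a cheap improvement and does not invalidate the study.

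**What to change.** - In 4.6.2 and step 5, record ventilator mode, set tidal volume or set pressure, PEEP and spontaneous breathing (Y/N) at both the pre-bolus and post-bolus readings.
- In 4.8, pre-specify a sensitivity analysis that repeats the AUROC and threshold results in boluses with unchanged set parameters and no spontaneous breaths at either reading. Define stability on set values: peak pressure under volume control, or delivered tidal volume under pressure control, can drift without any change of setting. For the same reason, mandatory exclusion for a change in any ventilator field would be unworkable and could remove many boluses from a study supplied with 30 probes.
- Under Aim III, report boluses with spontaneous breaths separately, and state that lower accuracy there will not be attributed to the index alone, because the reference depends on the same factor.

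The cost is a few more fields per bolus, completed by the investigator already in the room, and a sensitivity set smaller than the main one. Patient care does not change. Post-bolus ventilator readings that are not taken at the time may be impossible to recover later.

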4.5 Decision for volume expansion

All children receive a 10 ml/kg crystalloid bolus immediately after induction. The need/decision for a fluid bolus will be determined by the anesthesiologist based on clinical judgement. Currently, the anesthesiologist places an arterial line at the beginning of the case and using pulse pressure variability, HR, SBP, MAP, urine output, and blood loss determines whether or not a fluid or blood bolus is appropriate. Data collected from the CardioQ-EDM, CipherOx-CRI, and bedside ultrasound will not be provided to the care team.

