Reporting bias will be minimized by limiting interactions between the study team and OR team. Furthermore, as all children receive a bolus prior to incision, independent of available indices used to assess intravascular volume status, bias should be minimized for this fluid bolus. As these devices are experimental in this patient population, anesthesiologists will be blinded to hemodynamic data generated by the CardioQ-EDM, bedside ultrasound, and CipherOx CRI. If data is needed in an emergent setting, the subject will be excluded from analysis. Although recorded measurements from the Cardio-Q EDM monitor will be visible to the study team, IVC measurements will be stored and calculated post-hoc by a co-investigator blinded to whether or not the subject is or is not fluid responsive. Additionally, a trained statistician not involved in data collection will be paid for analysis. It should also be noted at [name] is a paid officer of CipherOx but will not be involved in the data collection and analysis.

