4.9.2 CardioQ-EDM Contraindications

- Doppler probes (DP240 and I2n) should not be placed in patients under 16 years of age. We will be using the KDP72 probe
- Do not use where nasal injuries are apparent or may have occurred.
- Do not use where nasal polyps exist.
- Do not use where there are circumstances of facial trauma.
- Do not use where there is a risk of brain injury.
- Do not use in patients undergoing intra-aortic balloon pumping.
- Do not use with carcinoma of the pharynx, larynx or esophagus.
- Do not use with aneurysms of the thoracic aorta.
- Do not use with tissue necrosis of the esophagus or nasal passage.
- Do not use in close proximity to laser surgery.
- Do not use in patients with pharyngo-oesophago-gastric pathology and/or severe bleeding diatheses.

5. Specific Aims:

Aim I: Define fluid responders based on aortic ΔV_{peak} : Among infants undergoing cranial vault reconstruction for craniosynostosis, we aim to determine the proportion who respond to clinically administered fluid or blood products defined by pre- and post-fluid challenge EDM $\Delta V_{Peak} >10\%$.

Mock-up Table 1: Demographics of Responders and Non-Responders to Initial 10 mL/kg bolus prior to surgical incision

Variable	Responders	Non-Responders	P-value
Demographics			
Age			
Weight			
Height			
BMI			
Gender			
Ethnicity			
Duration of NPO status			
Associated syndrome			

Legend: BMI, body mass index; npo, nil per os

Aim II: Calculate the PPV, NPV, sensitivity, specificity, and optimal threshold for CRI and collapsibility index as tools to prediction fluid responder

Protocol #: 18-2513

PI: [name]

[figure not shown]
Version date: 07/01/2019

		Fluid Responsive	
		Yes	No
CRI Threshold	+	True Positive	False Positive
	-	False Negative	True Negative

		Fluid Responsive	
		Yes	No
CI Threshold ($\geq 15\%$)	+	True Positive	False Positive
	-	False Negative	True Negative

Performance will also be calculated for heart rate, systolic blood pressure, mean arterial pressure, pulse pressure variability and stroke volume variability. Two separate analyses will be performed – one for the 10 ml/kg protocolized bolus provided immediately after induction and one accounting for all boluses provided.

Mock-up Figure

Mock-up Table 2 – Performance at predicting fluid responsiveness

Variable	Correlation (r)	AUC
IVC CI		
CRI		
SBP		
PPV		
SVV		
MAP		
HR		

Protocol #: 18-2513

PI: [name]

Version date: 07/01/2019

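### Excluding the whole child when device data are needed in an emergency discards boluses already measured under blinding; a cut-off at the time of disclosure would keep them

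*Combined protocol and SAP*

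**What the plan says.** Section 4.7 (Data Blinding) provides that "anesthesiologists will be blinded to hemodynamic data generated by the CardioQ-EDM, bedside ultrasound, and CipherOx CRI". It then states the exception: "If data is needed in an emergent setting, the subject will be excluded from analysis". The exclusion applies to the subject. The available text does not retain earlier boluses, ask for these exclusions to be counted, or plan a sensitivity analysis.

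Four other places bear on it:

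- Section 4.5: "All children receive a 10 ml/kg crystalloid bolus immediately after induction". Section 4.7 adds that, because this bolus is given "independent of available indices used to assess intravascular volume status, bias should be minimized for this fluid bolus".
- Section 4.4, on repeated challenges: "If more than one fluid bolus is administered at least 30 minutes apart, they will be reported as individual events".
- Section 5, under Aim II and again under Aim III, plans two analyses: "one for the 10 ml/kg protocolized bolus provided immediately after induction and one accounting for all boluses provided".
- Section 4.3.2, on vasopressor support: "fluid boluses administered during dosage adjustments will be excluded from analysis". There the child stays in and only the affected boluses go.

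**The concern.** The rule is wider than its purpose. Blinding matters because an anesthesiologist who sees the device readings might give or withhold later fluid in response to them. Fluid already given, with its measurements already taken, is beyond that influence. A child whose emergency comes midway through surgery nevertheless loses the first-bolus record and any later bolus completed beforehand.

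There is also a question of selection. A child for whom extra hemodynamic data are wanted urgently is plausibly less stable than the rest. The background section says these tools need validation in hypovolemic children with significant blood loss. Losing some of those children could shift the Aim I proportion and narrow the range over which the compensatory reserve index (CRI) and collapsibility index (CI) are tested in Aim II.

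**Working it through.** **Step 1: what disclosure can affect.** The steps in section 4.6 put the baseline readings before the protocolized bolus and the repeat readings shortly after it (two minutes in section 4.6, five in section 4.4). Section 4.7 places this bolus before incision. An emergency later in the operation therefore follows a complete first-bolus record. The same holds for any later bolus whose readings were finished before disclosure. If the emergency precedes any completed bolus, nothing valid is lost for that child.

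**Step 2: consistency.** Section 4.3.2 handles a disturbance by dropping the affected boluses; section 4.7 handles one by dropping the child. No reason is given for the difference.

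**Step 3: size for the first-bolus proportion.** The plan states no figure to reproduce. Inputs:

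- 30 children. This is an assumption, taken from the 30 probes in section 4.2; it is not a stated sample size.
- 15 first-bolus responders, from Hypothesis Ia (about half).
- k children excluded, of whom a share q are responders. Both are assumed.

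Proportion after exclusion = (15 − kq)/(30 − k).

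| k | q = 1 | q = 0.8 | q = 0.5 | q = 0 |
|---|---|---|---|---|
| 1 | 14/29 = 48.3% | 14.2/29 = 49.0% | 14.5/29 = 50% | 15/29 = 51.7% |
| 3 | 12/27 = 44.4% | 12.6/27 = 46.7% | 13.5/27 = 50% | 15/27 = 55.6% |
| 5 | 10/25 = 40.0% | 11/25 = 44.0% | 12.5/25 = 50% | 15/25 = 60.0% |

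The shift can go either way and is nil when the excluded children respond at the same rate as the rest. For scale, the 95% Wilson interval for 15/30 is about 33% to 67%.

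**Step 4: size for the AUROC.** At the hypothesized AUROC of 0.9, the Hanley-McNeil standard error is the square root of [A(1 − A) + (m − 1)(B − A²) + (n − 1)(C − A²)]/(mn), where A = 0.9, B = A/(2 − A), C = 2A²/(1 + A), m is the number of responders and n the number of non-responders. With 15 and 15, the 95% half-width is 1.96 × 0.0597 = 0.117. If all those excluded are responders, it becomes 0.120, 0.129 and 0.140 for k = 1, 3 and 5. In a deliberately extreme binormal simulation (4,000 runs) that removes the responders with the most extreme index values, the mean AUROC falls from 0.90 to about 0.89, 0.88 and 0.85.

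**Step 5: how often the rule would act.** The chance of at least one exclusion among 30 children is 1 − (1 − p)^30. This is 26% at an emergency rate of 1%, 79% at 5% and 96% at 10%. These rates are assumed; the documents give none.

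**The case against.** The strongest case for leaving the rule alone has four parts.

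*The trigger may hardly ever occur.* The anesthesiologist already has the arterial line, vital signs, urine output and blood loss. The devices are experimental in this population. CI is calculated, and CRI data interpreted, after the event. This stands as a limit on size: the rule may never act.

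*Whole-child exclusion is conservative.* CI is calculated later from stored loops, and a small team shares the scanning and device work, so an emergency disclosure might colour the later reading of earlier loops. This does not rescue the rule. Section 4.7 requires the reader to be blind to responsiveness, and disclosure to the care team does not by itself break that.

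*The bolus is not uniformly the unit of analysis.* Section 4.4 defines responders as children, and the first-bolus analysis has one record per child. That is correct, but that single record is complete before any later emergency.

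*Bias is not shown.* A reader might infer that the rule removes the most unstable children and pulls the responder proportion down. The documents do not support this. The text says only that data are needed in an emergent setting; it names no hemodynamic crisis, and the trigger is not defined by the bolus response. Nothing links a later emergency to the response to the first bolus.

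Larger shifts can be constructed for the all-bolus figure. With 30 children, three boluses each on average and 45 of 90 responsive, removing two children with four responsive boluses each gives (45 − 8)/(90 − 8) = 37/82 = 45.1%. If half of those eight boluses were responsive, the result is 41/82 = 50%. The example also pools first boluses, whereas Hypothesis Ib concerns only subsequent ones. And it counts all eight as avoidable losses, although a disclosure cut-off would recover only those measured beforehand.

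**Conclusion.** The point holds as a defect in the exclusion rule. Section 4.7 needlessly discards validly blinded records, most clearly the protocolized first bolus, and is inconsistent with section 4.3.2. That conclusion needs no assumption about response rates; it requires only that an emergency follow at least one completed bolus.

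Selection bias is possible but not established. The excluded children are likely to be among the less stable, yet the direction and size of any effect are unknown. Under the assumed 30 children and 15 responders, excluding 1 to 5 leaves the first-bolus proportion at 50% if half of them are responders, and lowers it to 48% to 40% if all are. One exclusion matters little; three to five, all or mostly responders, would be material. Parts of the protocol's front matter and background were not available, so a sample size stated there cannot be ruled out.

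The change is worth making because it is cheap, but the trial can run without it.

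**What to change.** Replace the sentence in section 4.7 with:

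*If device data are disclosed to the care team, the time is recorded; boluses given from disclosure onward are excluded from the primary analysis, and boluses whose pre- and post-bolus measurements were completed before disclosure are retained.*

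State that a bolus still under way or not yet fully measured at disclosure counts as excluded. Report the number of children and boluses affected, separately for the first-bolus and all-bolus analyses. Add a sensitivity analysis including all measured boluses. This last item is the part that addresses the narrowed range of hypovolemia, since the primary rule still drops boluses from disclosure onward.

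The cost is a short edit to section 4.7, one extra time on the data collection form (fluid and vasopressor times are already recorded under section 4.6.4) and one additional analysis. The downside is that some children contribute partial records. Emergency access to the data and clinical care are unchanged.
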